8.3 ADVERSE EVENT DEFINITIONS

Adverse Event (AE) – An AE is any untoward (unwanted) medical occurrence in a patient or clinical investigation subject administered a test article whether or not caused by the test article or treatment. An AE can therefore be any unfavorable or unintended sign (including an abnormal finding), symptom, or disease temporally associated with the use of the test article whether or not related to the test article.

An AE includes any condition (including a pre-existing condition) that: 1) was not present prior to study treatment, but appeared or reappeared following initiation of study treatment; or 2) was present prior to study treatment, but worsened during study treatment. This would include any condition resulting from concomitant illnesses, reactions to concomitant medications, or progression of disease states. Pregnancy should be documented as an adverse event and should be reported to the clinical monitor and to the Sponsor immediately upon learning of the event.

Serious Adverse Event (SAE) – An SAE is any untoward medical occurrence that:

- Results in death
- Is life threatening
- Requires in-patient hospitalization or prolongation of existing hospitalization
- Results in persistent or significant disability/incapacity (i.e., a significant persistent or permanent change, impairment, damage, or disruption to the subject's body)
- Is a congenital anomaly/birth defect, or
- Requires intervention to prevent permanent damage (the use of the investigational product resulting in a condition which requires medical or surgical intervention to preclude permanent impairment of the body structure or a body function). Important medical events that may not result in death, be life-threatening, or require hospitalization may be considered an SAE when, based upon appropriate medical judgment, they may jeopardize the patient or subject and may require medical or surgical intervention to prevent one of the outcomes listed in the above definition.

Diagnoses and conditions that are considered Serious Adverse Events include:

- Microbial Keratitis (MK)
- Iritis
- Permanent decrease in best spectacle corrected visual acuity equivalent to 2 acuity lines or greater
- Central Corneal Opacity
- Central Corneal Neovascularization
- Uveitis
- Endophthalmitis
- Hypopyon
- Hyphemia
- Penetration of Bowman's Membrane
- Persistent Epithelial Defect
- Limbal cell Damage leading to Conjunctivalization

Significant Adverse Events – Those events that are usually symptomatic and warrant discontinuation (temporary or permanent) of the test article (excluding Serious Adverse Events). Diagnoses and conditions that are considered Significant Adverse Events include the following:

- Contact Lens Induced Peripheral Ulcer (CLPU)
- Significant Infiltrative Events (SIE)
- Superior Epithelial Arcuate Lesions (SEALs)
- Any Temporary Loss of ≥ 2 Lines of BSCVA
- Other grade 3 or higher corneal findings, such as abrasions or edema
- Any corneal event which necessitates temporary lens discontinuation ≥ 2 weeks

- Non-contact lens related corneal events - e.g. EKC (Epidemic Keratoconjunctivitis)
- Asymptomatic Corneal Scar

Non-Significant Adverse Events – Those conditions that are usually asymptomatic and usually do not warrant discontinuation (temporary or permanent) of the test article. However, the Investigator may choose to treat as a precautionary measure. Diagnoses and conditions that are considered Non-Significant Adverse Events include the following:

- Non-significant Infiltrative Event
- Contact Lens Papillary Conjunctivitis
- Superficial Punctate Keratitis
- Conjunctivitis: Bacterial, Viral, Allergic
- Blepharitis
- Meibomianitis
- Contact Dermatitis
- Localized Allergic Reactions
- Any corneal event not explicitly defined as serious or significant adverse event, which necessitates temporary lens discontinuation < 2 weeks

Adverse Device Effect (ADE) – A sub-set of AEs, and include only those adverse events that are cause by or related to the investigational device or study procedure.

Unanticipated Adverse Device Effect (UADE) – Any serious adverse effect on health or safety or any life-threatening problem or death caused by, or associated with, the test article, if that effect, problem, or death was not previously identified in nature, severity, or degree of incidence in the investigational plan, investigator’s brochure or protocol, or any other unanticipated serious problem associated with the test article that relates to the rights, safety and welfare of subjects.

Causality Assessment – A determination of the relationship between an adverse event and the test article. The test article relationship for each adverse event should be determined by the investigator using these explanations:

- Not Related- An adverse event that is not related to the use of the test article.
- Doubtful – An adverse event for which an alternative explanation is more likely, e.g. concomitant treatment, concomitant disease(s), or the relationship of time suggests that a causal relationship is not likely.
- Possible – An adverse event that might be due to the use of the test article. An alternative explanation, e.g. concomitant treatment, concomitant disease(s), is inconclusive. The relationship in time is reasonable. Therefore, the causal relationship cannot be excluded.
- Probable – An adverse event that might be due to the use of the test article. The relationship in time is suggestive (e.g. confirmed by de-challenge). An alternative explanation is less likely, e.g. concomitant treatment or concomitant disease(s).
- Very Likely – An adverse event that is listed as a possible adverse effect (device) or adverse reaction (drug) and cannot be reasonably explained by an alternative explanation, e.g. concomitant treatment of concomitant disease(s). The relationship in time is very suggestive, e.g. it is confirmed by de-challenge and re-challenge.

Severity Assessment – A qualitative assessment of the degree of intensity of an adverse event as determined by the investigator or reported to him/her by the subject. The assessment of severity is made irrespective of test article relationship or seriousness of the event and should be evaluated according to the following scale:

- Mild – Event is noticeable to the subject, but is easily tolerated and does not interfere with the subject’s daily activities.

- Moderate – Event is bothersome, possible requiring additional therapy, and may interfere with the subject’s daily activities.
Severe – Event is intolerable, necessitates additional therapy or alteration of therapy and interferes with the subject’s daily activities.

8.4 METHODS FOR ASSESSING, RECORDING, AND ANALYZING SAFETY

The recording and documenting of adverse events (ocular and non-ocular) begin when the subjects are exposed to the test article or study treatment. Adverse events reported before the use of test article or start of study treatment should be recorded as medical history. Untoward medical events reported after the subject’s exit from the study will be recorded as adverse events at the discretion of the Investigator.

All adverse events observed by the Investigator; reported by the subject spontaneously; or in response to direct questioning; will be recorded in the source document. Such documentation will include a description of the adverse event, time of onset, duration of event, treatment regimen instituted, any referral to another health care provider (if needed), any new concomitant medications, outcome, ocular damage (if any), and likely etiology. Best Corrected Visual Acuity (BCVA) should be recorded prior to the report of an adverse event (as part of the baseline evaluation), upon report of the subject’s report of the adverse event, and after the adverse event has resolved. All adverse events will be followed in accordance with licensing requirements.

All adverse events will be documented in the appropriate section of the subject’s Case Report Form (CRF).

In conjunction with the medical monitor, the Investigator will evaluate adverse events to ensure the events are categorized correctly. Elements of categorization will include:

Seriousness (see definition in Section 8.3)

Expectedness – i.e. if the event was unexpected or unanticipated in that it was not previously identified in nature, severity, or degree of incidence (see definition in Section 8.3)

Causality or Relatedness – i.e. the relationship between the test article and the adverse event (not related; doubtful; possible; probable; very likely - see definition in Section 8.3)

Adverse Event Intensity or Classification – Adverse event intensity is used to assess the degree of intensity of the adverse event (mild, moderate, severe for all events). In addition Adverse event Classification is used to assess the severity of ocular adverse events (AE not requiring treatment, non-significant or significant see definition in Section 7.4).

Outcome – Fatal, not resolved, resolved, resolved with sequelae, resolving and unknown.

Actions Taken – None, temporarily discontinued, permanently discontinued, Other action taken

Upon finding an adverse event, the Principal Investigator will document the condition on the follow-up visit worksheet source document and in the CRF’s using photos or drawings (where appropriate) that detail size, location, and depth. He will also complete the Adverse Event Classification (AEC) Discovery form / eCRF. In addition, if an infiltrate(s) is present, he will complete the Corneal Infiltrate Assessment Form / eCRF. Where necessary, a culture of the corneal lesion will be collected to determine if the infection is microbial in nature. If cultures are collected, a source document note should be completed specifying the date of culture collection and laboratory utilized. An eCRF documenting this should be completed in a comment or unscheduled visit.

Complete description of all adverse events must be available in the source documents. All Adverse Events including local and systemic reactions not meeting the criteria for “serious adverse events” should be captured on the appropriate case report form or electronic data system. Information to be recorded, based on above assessment criteria, includes date site notified, event description, date and time of onset, investigator assessment of severity, relationship to Study Agent(s)/Intervention(s), and time of resolution/stabilization of the event. All adverse events occurring while on study must be documented appropriately regardless of relationship. Define a timeframe for CRF completion and entry of the adverse event information into the database, as applicable.

Any medical condition that is present at the time that the subject is screened should be considered as baseline and not recorded as an AE. However, if the condition deteriorates at any time during the study it should be recorded and reported as an AE.

Changes in the severity of an AE should be documented to allow an assessment of the duration of the event at each level of intensity to be performed. Adverse events characterized as intermittent require documentation of the onset and duration of each episode. Changes in the assessment of relationship to the Study Agent(s)/Interventions should also be clearly documented.

The investigator will notify the Sponsor of an adverse event by e-mail, facsimile, or telephone as soon as possible and no later than 24 hours from discovery for a serious / significant adverse event, and 2 days from discovery for a non-significant adverse event. In addition, a written report will be submitted by the Principal Investigator to the IRB/IEC according to their requirements (Section 12.3). Such a report should comment whether or not the adverse event was considered to be related to the test article.

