- ii. Distance monocular and binocular functional visual performance of the test and control contact lenses under night time conditions (2.5 cd/m²) for HC TCVA targets presented at 5° eccentricity;
- iii. Intermediate vision monocular and binocular functional visual performance of the test and control contact lenses under indoor conditions (50cd/m²) for HC TCVA targets presented at 5° eccentricity;
- iv. Distance monocular and binocular functional visual performance of the test and control contact lenses under night time conditions (2.5 cd/m²) for decreasing contrast targets presented at 20° eccentricity;
- v. Intermediate vision monocular and binocular functional visual performance of the test and control contact lenses under indoor conditions (50cd/m²) for decreasing contrast targets presented at 10° eccentricity;
- vi. Monocular and binocular horizontal visual fields when wearing the test and control contact lenses with an Esterman perimetry test.
- vii. Subjective rating of performance following driving simulation while wearing test and control contact lenses under night time conditions;
- viii. Subjective rating of performance following PC based reaction time game while wearing test and control contact lenses.

Study Design: The study will be a bilateral, subject-masked, randomized, 2x2 cross-over, non-dispensing pilot study involving three clinic visits. Investigators who collect measurements for primary and secondary endpoints will also be masked to the identity of the study lenses. Each subject will be assigned to a unique sequence of the lens types per the randomization scheme (Test/Control or Control/Test). Lenses will be worn for approximately three to four hours each with a 2-14 day washout period in between lenses.

Sample Size: A minimum of 20 eligible subjects are targeted to complete the study as the cohort population. Subjects who are found to be ineligible, or who are discontinued or incomplete, will be classified as the non-cohort population. The total number of subjects enrolled may not exceed 25 subjects,

except by joint agreement of the Investigator and Sponsor.

Eligibility Criteria:

Subjects should meet all study Inclusion Criteria as outlined below:

- 1) Healthy adult males or females 35 to 42 years of age (inclusive) with signed informed consent.
- 2) The subject is a current spherical soft contact lens wearer (defined as a minimum of 6 hours of DW for a minimum of 1 month prior to the study).

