4.5 RANDOMIZATION AND MASKING

The lenses will not be dispensed and will be worn in a bilateral and random fashion using a 2x2 cross-over design. Permuted block randomization will be used to minimize the potential for treatment imbalance. A block size of two (2) will be utilized. A computer-generated randomization scheme will be provided by the study biostatistician to randomly assign subjects to one of two possible lens wear sequences (Test/Control or Control/Test) in a 1:1 manner. The order of applied distance as well as luminance within distance (if applicable) during vision assessments will also be randomized for each subject within lens type. The same orders applied for the first lens type will be used for the second lens type.

The random scheme will be generated using the PROC PLAN procedure from SAS Software Version 9.4 or higher (SAS Institute, Cary, NC).

The study site must follow the randomization scheme provided and complete the enrollment according to the randomization list and not pre-select or assign subjects. The randomized assignment of subjects will be performed at the beginning of Visit 2. The following must have occurred prior to randomization:

- Informed consent has been obtained
- Subject meets all the inclusion / exclusion criteria
- Subject history and baseline information has been collected

This is a subject-masked study. Study participants will be masked with respect to the sequence of study lens wear to which they have been assigned. An unmasked investigator will insert and remove the study lenses so that the subject is not aware of the study lens type. The identity of the study lenses will be unmasked to the investigator who will record the lens fitting measurements. However, the identity of the study lenses will be masked to the investigator who will collect measurements for the study primary and secondary endpoints.

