13.	Vision Assessments	
Time Controlled Visual Acuity (TCVA) Measurements will be made at 4m using 2.5 and 250 cd/m² luminance, and at 67cm using 50 cd/m² luminance. The luminance requirements will be the same at the target and at the eye. Monocular and binocular visual performance will be measured for the following conditions:
 
 • Distance 2.5 cd/m² 
 ○ Central ○ 5 degrees eccentricity ○ 20 degrees eccentricity • Distance 250 cd/m² 
 ○ Central • Intermediate 50 cd/m² 
 ○ Central ○ 5 degrees eccentricity ○ 10 degrees eccentricity 
The order of luminances tested will be randomized.
 
Subjects will undergo a driving simulation test and subsequently make a subjective assessment of their visual performance.
 
Subjects will play computer based reaction time games and subsequently make a subjective assessment of their visual performance.
	Manual of Procedures
14.	Lens Removal	The contact lenses are removed and discarded.	

15.	Biomicroscopy	
Biomicroscopy will be performed OD and OS. Standard Slit Lamp Classification Scales will be used to grade the findings. For the limbal and conjunctival redness, 0.5 unit increments will be used in the grading.
	
Manual of Procedures
 
16.	Distance Spherocylindrical Refraction and Exit Visual Acuity	An optimal, binocular balanced distance spherocylindrical refraction will be performed. The distance visual acuity to the nearest letter will be recorded OD, OS and OU.	
Manual of Procedures
 
17.	Continuance	Indicate whether the subject will continue to the next visit. If not, proceed to Final Evaluation.	

Visit 3: Second Measurement Visit (2 to 14 days after Visit 2)			
Step	Descriptor	Details	Appendix
1.	Concomitant Medications/Treatments	Questions regarding the subjects' medications and/or treatments.	
2.	Subject Reported Ocular Symptoms	Record any symptoms or problems that the subject may experience with their habitual contact lenses, if applicable. Subject will not be asked about specific categories of complaints, but the severity or frequency will be recorded in the following categories: 
 • Burning/Stinging • Itchiness/Scratchiness • Dryness • Lens Awareness • Grittiness/Foreign Body Sensation • Redness • Irritation/Discomfort • Cloudy/Blurry/Hazy • Variable Vision • Other 	

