8.1 SAFETY PARAMETERS

The following safety parameters will be monitored and evaluated:

- Ocular physiology characteristics
- Lens fitting characteristics
- Adverse events
- Ocular symptoms
- Snellen distance visual acuity
- Reasons for discontinuation
- Reasons for unplanned lens replacement
- Quality Complaints

Safety parameters will be tabulated using frequency distribution tables and descriptive statistics. Adverse events will be listed by subject/eye. There will be separate summary tables for adverse events and infiltrative adverse events. Statistical methods for analyzing safety data, if any, are provided in section 9.

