Patients should be warned that serious adverse reactions such as ulcers or keratitis can arise very quickly and are more likely to occur if the patient does not follow the manufacturers recommendations for wearing times, replacement schedule, use of care products and lens cases. The patient should not wear the lens whilst sleeping, showering or swimming.

The eye care professional must ensure that the patient can remove their lenses before dispensing them and should advise the patient to remove the lenses and contact them immediately if any adverse reaction arises. The patient should attend regular after-care appointments.

CR-5856 Protocol v2.0 Amendment 1.0
Ensure that any sodium fluorescein has dissipated before inserting the lenses, due to lens absorption of the dye and increased infection risk.

IMPORTANT PATIENT INFORMATION

PRECAUTIONS:

- DO NOT exceed your recommended wearing time.
- DO NOT use the lenses after the recommended replacement date.
- DO NOT swim whilst wearing the lenses.
- DO NOT sleep whilst wearing the lenses.
- DO NOT allow tap water or saliva to come into contact with your lenses.
- DO NOT wear your lenses if your eyes are sore and/or red.
- DO NOT use lenses in saline only, always use a contact lens solution.
- DO NOT use lenses or solutions after their use by date.
- DO NOT wear lenses if you are using eye drops unless advised to by your eye care professional
- YOU SHOULD wash and dry hands (with clean lint free tissue or towel) before handling, inserting or removing the lens.
- YOU SHOULD rinse your lens case daily with saline or fresh contact lens solution and allow to air dry.
- YOU SHOULD replace your lens case on a regular basis.
- YOU SHOULD follow your eye care professional's instructions.
- YOU SHOULD attend regular after-care appointments with your eye care professional.

LENS CARE DIRECTIONS:

Correct care of your lenses is essential:

- Disinfect your lenses each time they are removed from your eyes to destroy harmful germs and to ensure safe and comfortable contact lens wear
- A separate cleaning and rinsing step may be recommended by your eye care professional to remove contaminants from the lens surface. In addition, your lenses may require periodic enzymatic cleaning to remove protein.
- Your eye care professional should recommend the lens care system most suitable to you.
- Ask your eye care professional before using any alternative lens care products.

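### Mandatory adverse event capture runs on after Visit 2 wear but stops at the same-visit Final Evaluation after Visit 3 wear, so delayed events after about half of each lens's exposures may go unrecorded

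*Combined protocol and SAP*

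**What the plan says.** Section 8.4 sets the start of recording: "The recording and documenting of adverse events (ocular and non-ocular) begin when the subjects are exposed to the test article or study treatment". It also sets the rule during the study: "All adverse events occurring while on study must be documented appropriately regardless of relationship". For events reported later the rule changes. Those reported after the subject's "exit from the study will be recorded as adverse events at the discretion of the Investigator".

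The schedule treats the two wear periods differently.

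- **After the Visit 2 lens.** The synopsis says "Lenses will be worn for approximately three to four hours each with a 2-14 day washout period in between lenses", and section 4.7.1 gives the same interval: "Visit 3: Second Measurement Visit (2 to 14 days after Visit 2". The subject remains on study during it. Visit 3 opens with medication and symptom questions, refraction with acuity, and biomicroscopy, all before the second lens goes in.
- **After the Visit 3 lens.** Sections 4.4.1 and 4.7.1 place the Final Evaluation (biomicroscopy, refraction with exit acuity, completion form) straight after lens removal. Section 4.4 plans three visits, and nothing is scheduled later.

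Section 4.4.1 does not agree with the 2 to 14 days. It says that visit intervals are not fixed and expects both measurement visits to fall within a month.

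On reporting, section 8.1 says "Adverse events will be listed by subject/eye" and adds separate summary tables for all adverse events and for infiltrative ones. Section 9.1 presents summaries by lens type and does not ask for a split by period. On masking, section 4.5 says "An unmasked investigator will insert and remove the study lenses so that the subject is not aware of the study lens type". A different, masked investigator collects the primary and secondary endpoints.

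**The concern.** Adverse events are a named safety parameter, summarised by lens. Each lens's row would pool exposures that had days of mandatory recording after the visit with exposures that had none, and nothing in the table would show it. An event that first appears after the subject goes home has a required route into the database if the lens was worn at Visit 2. If the lens was worn at Visit 3, it depends on the subject coming forward and on the Investigator choosing to record it.

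The lists in section 8.3 include microbial keratitis, peripheral ulcers and infiltrative events, and nothing in the documents confines their onset to clinic hours. The package insert in Appendix B warns that "serious adverse reactions such as ulcers or keratitis can arise very quickly". The follow-up duties in sections 6.3 and 8.5 concern problems or events already ongoing at the final visit, so they do not reach an event that starts afterwards.

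A rule that leaves recording to judgement is a second weakness. Section 8.4 does not say whether the Investigator who decides is masked to the lens last worn.

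**Working it through.** The documents give no event rate, safety precision or power figure, so there is no stated number to reproduce. The check counts exposures and shows what the shortfall means over an assumed range of risks.

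**Inputs from the documents.** 20 target completers, at most 25 enrolled unless both parties agree otherwise (section 9.2); 1:1 sequences in blocks of two (section 4.5); 2 to 14 days between measurement visits (synopsis, section 4.7.1).

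**Assumptions.** Exit means completion of the Final Evaluation, since the documents do not define it. Exposures are independent. A late event after Visit 2 wear is captured, and one after Visit 3 wear is not. The last assumption gives the worst case, because discretionary recording could recover some events.

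**Step 1: exposures affected.** With 20 completers there are 20 / 2 = 10 subjects per sequence. Each lens is therefore worn second in 10 of its 20 exposures, or 50%. If 25 completed, it would be 12 or 13 of 25, or 48% to 52%.

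**Step 2: mandatory post-visit observation per lens, 20 completers.**

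- As planned: 10 × 2 = 20 to 10 × 14 = 140 person-days, all from Visit 2 wear.
- If both periods had the same window: 20 × 2 = 40 to 20 × 14 = 280 person-days.

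**Step 3: what zero late events would show.** The one-sided 95% upper bound is 1 − 0.05^(1/n).

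- n = 10: 1 − 0.05^(1/10) = 25.9%.
- n = 20: 1 − 0.05^(1/20) = 13.9%.

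**Step 4: chance of capturing at least one late event per lens**, 1 − (1 − p)^n, where p is an assumed late-event risk per exposure.

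| Assumed p | 10 followed exposures | 20 followed exposures |
|---|---|---|
| 1% | 9.6% | 18.2% |
| 2% | 18.3% | 33.2% |
| 5% | 40.1% | 64.2% |
| 10% | 65.1% | 87.8% |

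**Step 5: direction between lenses.** Test and Control are each worn second in 10 exposures, so the loss in Steps 1 to 4 is the same for both. The unequal windows alone do not tilt the comparison.

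**The case against.** The strongest reply is that little is at stake. This is a non-dispensing pilot of visual performance in adapted wearers using CE-marked lenses. Each pair is worn once, on site, for three to four hours and then discarded. Adverse events are described, with no safety hypothesis. The insert's warning goes on to link such reactions to not following the manufacturer's instructions, and rapid onset is a weak argument for a two-week window. This stands as a reason to expect few events and to keep the remedy small. It does not explain why the two periods should have different recording rules.

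The interval after Visit 2 is also an imperfect benchmark. Section 4.4.1 says that intervals are not fixed. The Visit 3 symptom item refers to habitual lenses, and subjects are asked only to avoid lens wear on the day of a visit. Events in that interval cannot be credited cleanly to the study lens. This stands too. It affects attribution, and it rules out assigning every later event to the last study lens. Recording remains mandatory throughout that interval.

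A reader might infer four stronger things that the documents do not support:

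- **That the Visit 3 lens has no adverse event capture.** Events during wear, at the post-removal slit-lamp examination and at exit acuity must be recorded, and related events still ongoing are followed under section 8.5.
- **That later events are lost.** They may be recorded, but nothing requires it or prompts the report.
- **That the Test-Control comparison is biased.** The 1:1 sequences balance the gap. Bias could enter only through the discretion, and no passage says that an unmasked person exercises it.
- **That section 12.4 already covers a follow-up call.** The contact it describes is by health authorities and sponsor staff seeking consent for further safety evaluations. Routine calls by the site fall outside it.

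**Conclusion.** The concern holds as a gap in mandatory capture after the visit. For 10 of each lens's 20 exposures, required recording ends at the same-visit Final Evaluation. For the other 10 it continues until Visit 3. Delayed-onset events after the second wear may therefore go unrecorded. The consequences are lower sensitivity for both lenses and a capture window that is confounded with period. Bias between lenses is a possibility only, through the undefined masking of whoever decides.

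The share affected rests on the 1:1 allocation and on exit coinciding with the Final Evaluation. The 2 to 14 day figure depends on reconciling the synopsis and section 4.7.1 with section 4.4.1. The capture probabilities rest on assumed risks of 1% to 10% and on no post-exit event being recorded. The true late-event risk after one short wear may lie below that range, and the documents give no figure for it. The change is worth making because it is cheap and removes an avoidable difference in how the two periods are observed.

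**What to change.** 1. Reconcile the interval between the measurement visits across the synopsis, section 4.4.1 and section 4.7.1.
2. In section 8.4, replace the discretion clause with mandatory recording of every event reported within a fixed window after Visit 3, comparable to the reconciled interval.
3. At exit, ask subjects to report any problem in that window. Optionally, close the window with one brief contact by existing staff.
4. For each such event, record the study lens last worn and any habitual lens wear since. Assess causality under section 8.3, and do not attribute the event to the last study lens by default.
5. Tabulate adverse events by lens and period, so that any remaining difference in capture can be seen.

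The cost is a short amendment with the usual ethics review, possibly one added line in the consent form, and at most one contact for each of up to 25 subjects. With a 14-day window, database lock could come up to about two weeks later for the last subject.
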